#### **1.2.6.5 Clinical Trial Experience Using the Intravenous Formulation of MLN9708**

See the IB for descriptions of the 2 ongoing studies investigating IV MLN9708 in advanced solid tumors and advanced lymphoma (Studies C16001 and C16002, respectively).

#### **1.2.6.6 Clinical Trial Safety Experience: Pooled Intravenous and Oral Formulation**

The potential risks reported with MLN9708 use, pooled from the enrolling 7 phase 1 and phase 1/2 clinical studies (including both IV and PO formulations) are shown in Table 1-6. Although the predominant potential toxicities may be severe in some cases, they are largely

reversible and can be managed by routine clinical monitoring and standard medical interventions, which may include dose reduction or supportive care. There is also consistency in the type of TEAE reported regardless of the MLN9708 formulation, even though there are differences in the frequency and severity of the reported events. Over all, the weekly schedule is active and has milder toxicities than the twice-weekly schedule. The most frequent AEs, listed in Table 1-6, were anticipated based on nonclinical data and previous experience with bortezomib.

**Table 1-6 MLN9708 Potential Risks (Pooled Intravenous and Oral Formulations) as of 12 October 2011**

Adverse Drug Reactions	Thrombocytopenia Skin rash (Includes terms: erythematous, generalized, pruritic, macular, macula-papular, papular) Nausea, vomiting, diarrhea Fatigue
Potential Risks Reported (> 10%) Due to MLN9708 or Disease Under Study	Fever Anorexia, constipation, dehydration Anemia, neutropenia Headache Dizziness Upper Respiratory Infection, dyspnea, cough Chills Arthralgia Abdominal or back pain Peripheral edema

Please refer to the current MLN9708 Investigator's Brochure (IB) and Safety Management Attachment (SMA) for more information.

[figure not shown]
### 1.2.7 Potential Risks of MLN9708

Please refer to the current MLN9708 Investigator's Brochure (IB) and Safety Management Attachment (SMA).

### 1.3 Lenalidomide (CC-5013)

REVLIMID® (lenalidomide), a thalidomide analogue, is an immunomodulatory agent with anti-angiogenic properties. The chemical name is 3-(4-amino-1-oxo 1,3-dihydro -2H-isoindol-2-yl) piperidine-2,6-dione and it has the following chemical structure:

Chemical Structure of Lenalidomide

3-(4-amino-1-oxo 1,3-dihydro-2*H*-isoindol-2-yl)piperidine-2,6-dione

The empirical formula for lenalidomide is C13H13N3O3, and the gram molecular weight is 259.3.

Lenalidomide is off-white to pale-yellow solid powder. It is soluble in organic solvent/water mixtures, and buffered aqueous solvents. Lenalidomide is more soluble in organic solvents and low pH solutions. Solubility was significantly lower in less acidic buffers, ranging from about 0.4 to 0.5 mg/ml. Lenalidomide has an asymmetric carbon atom and can exist as the optically active forms S(-) and R(+), and is produced as a racemic mixture with a net optical rotation of zero.

REVLIMID® (lenalidomide) is available in 5 mg capsules for oral administration. Each capsule contains lenalidomide as the active ingredient and the following inactive ingredients: lactose anhydrous, microcrystalline cellulose, croscarmellose sodium, and magnesium stearate. The 5 mg capsule shell contains gelatin, titanium dioxide and black ink. The 10 mg capsule shell contains gelatin, FD&C blue #2, yellow iron oxide, titanium dioxide and black ink.

REVLIMID® (lenalidomide) is indicated for the treatment of patients with transfusion-dependent anemia due to Low- or Intermediate-1-risk myelodysplastic syndromes associated with a deletion 5q cytogenetic abnormality with or without additional cytogenetic abnormalities. Revlimid® is also approved in combination with dexamethasone for the treatment of patients with multiple myeloma that have received at least one prior therapy. All other uses are considered investigational.

### Clinical Pharmacokinetics and Pharmacodynamics

#### *Absorption:*

Lenalidomide, in healthy volunteers, is rapidly absorbed following oral administration with maximum plasma concentrations occurring between 0.625 and 1.5 hours post-dose. Co-administration with food does not alter the extent of absorption (AUC) but does reduce the maximal plasma concentration (Cmax) by 36%. The pharmacokinetic disposition of lenalidomide is linear. Cmax and AUC increase proportionately with increases in dose. Multiple dosing at the recommended dose-regimen does not result in drug accumulation.

Pharmacokinetic sampling in myelodysplastic syndrome (MDS) patients was not performed. In multiple myeloma patients maximum plasma concentrations occurred between 0.5 and

4.0 hours post-dose both on Days 1 and 28. AUC and Cmax values increase proportionally with dose following single and multiple doses. Exposure (AUC) in multiple myeloma patients is 57% higher than in healthy male volunteers.

### 1.3.1 Pharmacokinetic Parameters

#### **Distribution:**

In vitro (C)-lenalidomide binding to plasma proteins is approximately 30%.

#### **Metabolism and Excretion:**

The metabolic profile of lenalidomide in humans has not been studied. In healthy volunteers, approximately two-thirds of lenalidomide is eliminated unchanged through urinary excretion. The process exceeds the glomerular filtration rate and therefore is partially or entirely active. Half-life of elimination is approximately 3 hours.

#### Supplier(s)

Revlimid® (lenalidomide) will be billed to the patients insurance through commercial supply to study participants.

#### Dosage form

Lenalidomide will be supplied as capsules for oral administration.

#### Packaging

. Bottles will contain a sufficient number of capsules for one cycle of dosing.

#### **Storage**

Lenalidomide should be stored at room temperature away from direct sunlight and protected from excessive heat and cold.

#### **Prescribing Information**

Lenalidomide will be provided in accordance with the RevAssist® program. Per standard RevAssist® requirements all physicians who prescribe lenalidomide for research subjects enrolled into this trial, and all research subjects enrolled into this trial, must be registered in and must comply with all requirements of Celgene's RevAssist® program. **Only enough lenalidomide for one cycle of therapy will be supplied to the patient each cycle.**

#### **Special Populations:**

*Patients with Renal Insufficiency:* The pharmacokinetics of lenalidomide in MDS patients with renal dysfunction has not been determined. In multiple myeloma patients, those with mild renal impairment had an AUC 56% greater than those with normal renal function. (See **PRECAUTIONS: Renal Impairment**).

*Patients with Hepatic Disease:* The pharmacokinetics of lenalidomide in patients with hepatic impairment has not been studied.

*Age:* The effects of age on the pharmacokinetics of lenalidomide have not been studied.

*Pediatric:* No pharmacokinetic data are available in patients below the age of 18 years.

*Gender:* The effects of gender on the pharmacokinetics of lenalidomide have not been studied.

*Race:* Pharmacokinetic differences due to race have not been studied.

### **1.3.2 Deep Venous Thrombosis and Pulmonary Embolism**

This drug has demonstrated a significantly increased risk of DVT and PE in patients with multiple myeloma who were treated with REVCLIMID® (lenalidomide) combination therapy. Patients and physicians are advised to be observant for the signs and symptoms of thromboembolism. Patients should be instructed to seek medical care if they develop symptoms such as shortness of breath, chest pain, or arm or leg swelling

### **OTHER ADVERSE EVENTS**

Most frequently reported adverse events reported during clinical studies with lenalidomide in oncologic and non-oncologic indications, regardless of presumed relationship to study medication include: anemia, neutropenia, thrombocytopenia and pancytopenia, abdominal pain, nausea, vomiting and diarrhea, dehydration, rash, itching, infections, sepsis, pneumonia, UTI, Upper respiratory infection, cellulitis, atrial fibrillation, congestive heart failure, myocardial infarction, chest pain, weakness, hypotension, hypercalcemia, hyperglycemia, back pain, bone pain, generalized pain, dizziness, mental status changes, syncope, renal failure, dyspnea, pleural effusion, pulmonary embolism, deep vein thrombosis, CVA, convulsions, dizziness, spinal cord compression, syncope, disease progression, death not specified and fractures.

### **1.3.3 INDICATIONS AND USAGE:**

Revlimid® (lenalidomide) is indicated for the treatment of patients with transfusion-dependent anemia due to Low- or Intermediate-1-risk myelodysplastic syndromes associated with a deletion 5q cytogenetic abnormality with or without additional cytogenetic abnormalities. Revlimid® is also approved in combination with dexamethasone for the treatment of patients with multiple myeloma that have received at least one priortherapy.

### 1.3.4 Clinical Experience

A Phase I study in subjects with refractory or relapsed MM was conducted to identify the maximum tolerated dose (MTD) and to evaluate the safety of lenalidomide given orally for up to 4 weeks at 5 mg/day, 10 mg/day, 25 mg/day and 50 mg/day. Secondary objectives included evaluation of response to lenalidomide, as well as pharmacokinetics and identification of surrogate markers to aid in defining mechanisms of action. Subjects who tolerated study drug with acceptable toxicity and were without disease progression were permitted to continue on therapy beyond 28 days as part of an extension phase for over 1 year. Twenty-seven subjects were enrolled, of whom 15 had undergone prior autologous stem cell transplantation and 16 had received prior thalidomide, with a median of 3 prior regimens (range 2-6). All subjects had relapsed MM and 18 (72%) were refractory to salvage therapy. Two subjects were removed from study on the first day of treatment due to rapid disease progression, which resulted in renal dysfunction and rendered them ineligible. The first group of 3 subjects were treated for 28 d at 5 mg/d without any dose limiting toxicity (DLT). The second cohort of 3 subjects commenced therapy at 10 mg/day. In one subject, DLT was encountered with grade (G) 2 fever as well as G3 leukopenia and neutropenia, resulting in removal from study before day 28. Two subjects tolerated drug. Three additional subjects were treated at 10 mg/day with no attributable toxicity within the first 28 days. In the third cohort of 3 subjects at 25mg/day, drug was well tolerated within the first 28 days but G3 thrombocytopenia and G3 and G4 neutropenia occurred during the second month, resulting in 2 subjects being removed from study. In the fourth cohort at 50mg/day, the first 3 subjects tolerated treatment without DLT in the first 28 days and a subsequent 10 subjects also tolerated drug without DLT within the first 28 days. However, subsequent G3 thrombocytopenia and G3/4 neutropenia in the extension phase has prompted dose reduction and GCSF support in all subjects. No significant somnolence, constipation or neuropathy has been seen in any cohort. Median duration of therapy is currently 4 months [range 2 weeks – 14 months] and 11 subjects continue on treatment. Maximal protein reductions seen during therapy in subjects who have received  $\geq 28$ d of treatment are summarized below:

**Table 1-2 M Protein Reductions in a Phase I Study with Lenalidomide**

Dose [mg]	Pts [n]	< 25%	$\geq 25\%$	< 50%	> 50%	Progression

5	3	-	2	1	-
10	5	-	-	1	4
25	3	1	2	-	-
50	13	3	5	4	1
Subtotals	24	4 (17%)	9 (37%)	6 (25%)	5 (21%)

Thus, best responses in protein of  $\geq 25\%$  have been seen in 15 of 24 evaluable pts (63%), and a  $<25\%$  reduction has been seen in 4 subjects to achieve stable disease or better in 19 of 24 (79%). Pharmacokinetics [days 1-4, and 28] have been completed in 24 subjects and reveal rapid absorption (t max: 1-1.5 h); monophasic elimination (t  $\frac{1}{2}$ : 3.1-4.2 h), and low to moderate inter-subject variability for AUC (11-52%) and C max (3-33%). Furthermore, there was no significant accumulation by day 28. In conclusion, these studies suggest Lenalidomide at the dose levels studied has anti-tumor activity, continuous pharmacokinetics (PK) with convenient daily oral dosing and acceptable toxicity in subjects with relapsed and refractory multiple myeloma. (Richardson et al., 2002)

Given the myelosuppression beyond day 28 seen in all subjects at 50 mg/day, this dose was considered to be the DLT, and thus the 25 mg/day dose level as a continuous daily schedule of administration was considered MTD. Given the activity of the drug seen at lower dose levels and the PK characteristics observed, 30 mg/day in divided or single daily dose was assessed for activity and safety, and to determine whether a divided dose schedule is superior. In addition, a 3-week on and one-week off schedule was assessed to determine if a cycling schedule would decrease the myelosuppression that was observed in earlier trials with daily dosing. In this phase II study, 70 subjects with relapsed and refractory Myeloma were enrolled at several centers in the U.S. Richardson et al reported that 26% of subjects required dose reduction due to myelosuppression in this study. Responses that were observed included 4% of subjects with complete responses, 17% with partial responses and 33% with minimal responses. Progressive disease occurred in 15% of subjects (Richardson et al., 2002). It was concluded that daily dosing was better tolerated than twice daily dosing because of a lower incidence and severity of myelosuppression.

Data from two phase III trials comparing lenalidomide + dexamethasone to single agent dexamethasone in patients with relapsed and/or refractory multiple myeloma were presented at the 10th International Multiple Myeloma Workshop in Sydney Australia (Weber et al., 2005; Dimopoulos et al., 2005). Patients who had received 1-3 prior therapies, and progressing on their last therapy were randomized to receive lenalidomide, 25 mg/d x 21 d, placebo d22-28 plus dexamethasone, 40 mg, d 1-4, 9-12, 17-20, q 28d or placebo daily x 28 d plus dexamethasone, 40 mg, d 1-4, 9-12, 17-20, q28d. The responses reported are summarized in Table 1-4 while the incidence of DVT and pulmonary embolism are summarized in Table 1-5. Anemia, thrombocytopenia, neutropenia, fatigue, neuropathy, and constipation were also observed more often in lenalidomide + dexamethasone group compared to dexamethasone only group, however these events were generally manageable.

**Table 1-3 Response Rates in Phase III Trials of Relapse refractory MM (Celgene MM-009 and MM-010)**

	Weber et al (ASCO 05 oral presentation)			Dimopoulos et al (ASH 2005 # 6)		
	Lenalidomide + Dexa (n=170)	Dexa Alone (n=171)	P Value	Lenalidomide + Dexa (n=176)	Dexa Alone (n=175)	P Value
Overall Response Rate (%)	61%	23%	≤0.001	59%	24%	≤0.001
TTP (mo.)	15	5	≤0.00001	11.3	4.7	≤0.00001

**Table 1-4 DVT & PE Risks in Phase III Trials of Relapse refractory MM (Celgene MM-009 and MM-010)**

	Weber et al*		Dimopoulos et al*	
	Lenalidomide + Dexa	Dexa Alone	Lenalidomide + Dexa	Dexa Alone

Deep Vein Thrombosis (%)	13.5	3.5	5.0	5.0
Pulmonary Embolism (%)	2.9	0.6	4.0	1.0

Oral presentation from Dimopoulos ASH 2005

#### **1.4 Study Rationale and Selection of Drug Doses**

There have been significant advances in the management of multiple both in the relapsed/refractory, newly diagnosed patients with subsequent improvements in response rates, and survival. The role of maintenance therapy and the optimal regimen post autologous stem cell transplant (ASCT) in the myeloma paradigm continues to evolve.

Both lenalidomide and bortezomib have been evaluated as maintenance therapy post ASCT.

CALBG 100104 was a phase III trial which randomized patients post ASCT to maintenance lenalidomide 10 mg/day or placebo. Maintenance lenalidomide on an intention to treat analysis lead to a 20.5 month improvement in time to progression (TTP) from 21.8 months to 42.3 months with 17 months of followup. This benefit in TTP was seen in patients with prior thalidomide or lenalidomide based induction therapies. The major toxicity was hematologic toxicity, with 43% of patients experiencing grade 3/4 neutropenia, 13% with G3/4 thrombocytopenia with 12% patients discontinuing therapy due to any adverse event.

A second trial, IFM 2005-02 trial randomized patients post ASCT to placebo or 2 months of consolidation with lenalidomide 25 mg/day for days 1-21 for 2 months followed maintenance lenalidomide 10-15 mg daily. This led to an improvement in progression free survival post transplant from 24 months to 42 months.

These two trials have established maintenance lenalidomide as an important therapeutic option leading to significant improvements in PFS and potentially overall survival.

The combination of proteasome inhibitors and lenalidomide have been studied preclinically demonstrating synergy and clinically in both induction therapy as well as relapsed myeloma with promising activity.

The combination also warrant further exploration as the maintenance therapy post transplant. Specifically the addition of oral MLN 9708 to lenalidomide, is attractive as an all oral regimen with expected improvements in PFS/TTP compared to single agent lenalidomide.

The dosage of lenalidomide will be based on the CALBG experience with 10 mg and modified as tolerated. The dose of MLN 9708 will be based on the single agent experience as well as combination studies. We will start 3 mg orally on day 1, 8, and 15 and dose modifications based on tolerability.

**2. STUDY OBJECTIVES****2.1 Primary Objective**

- Establish safety and efficacy of oral MLN 9708 and lenalidomide in the maintenance setting post ASCT in myeloma patients
- Primary endpoint:
  - Progression free survival (PFS)

**2.2 Secondary Objectives**

The secondary objectives of this study are to:

- Incidence of secondary primary malignancy
- Evaluate the best response rate (sCR/nCR/VGPR/PR)
- Evaluate time to progression
- Evaluate time to next therapy
- Evaluate the tolerability and toxicity
- Evaluate MDASI- Myeloma symptom evaluation.

### **3. INVESTIGATIONAL PLAN**

#### **3.1 Overall Design and Plan of the Study**

Eligible patients will be enrolled and maintenance therapy on protocol no less than 60 days and must be initiated no more than 180 days post ASCT.

Patients will have standard restaging studies prior to initiation of therapy.

Standard post transplant therapy per institutional guidelines will be unaltered including prophylaxis therapy, vaccinations and restaging.

Patients who have completed ASCT and meet eligibility criteria will initiate maintenance therapy based on time on enrollment either in the phase dose escalation or expansion portion of trial.

Patients' clinical laboratory values and toxicity must be as specified below within 5 days before the first dose of study drug:

- Platelet count  $\geq 100,000/\text{mm}^3$
- Neutrophil count  $\geq 1000/\text{mm}^3$  (No growth factors within 5 days)
- Total bilirubin  $\leq 1.5 \times \text{ULN}$
- Alanine aminotransferase (ALT) and aspartate aminotransferase (AST)  $\leq 3 \times \text{ULN}$
- Creatinine  $< 2.5 \text{ mg/dL}$

Recovered (ie,  $\leq$  Grade 1 toxicity) from the reversible effects of autologous stem cell transplant.

Each cycle will be defined as a 28 day cycle. Drug holidays and break in therapy including those due to holidays, physician discretion and drug delivery are allowed as needed. Study drug will begin at Lenalidomide (10 mg/day); after three cycles , provided the ANC is  $\geq$  1000/ $\mu$ L, platelet count  $\geq$  100,000/ $\mu$ L, and all nonhematologic toxicity is  $\leq$  grade 1, then the dose may be increased to 15 mg/day at discretion of physician.

MLN 9708 will be dosed at 3 mg flat dose on days 1, 8, 15 administered orally.

Patients will be allowed to receive radiotherapy for palliation of symptoms during the course of maintenance therapy

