#### **3.2.1 Inclusion Criteria**

Each patient must meet all of the following inclusion criteria to be enrolled in the study:

1. Patient must have undergone autologous stem cell transplantation, with melphalan as a preparative regimen, within 12 months of initiation of induction therapy for newly diagnosed myeloma.
2. Time to initiation of maintenance therapy.

Patients may start maintenance therapy as early as 60 days post transplant and up to - 180 post transplant; as long as they meet the following criteria:

- Platelet count  $\geq$  100,000/mm^3
- Neutrophil count  $\geq$  1000/mm^3. (No growth factors within 5 days)
- Total bilirubin  $\leq$  1.5  $\times$  ULN
- Alanine aminotransferase (ALT) and aspartate aminotransferase (AST)  $\leq$  3  $\times$  ULN
- Creatinine  $<$  2.5 mg/dL
- Recovered (ie,  $\leq$  Grade 1 toxicity) from the reversible effects of autologous

3. Patients whose primary therapy was changed due to suboptimal response or toxicity will be eligible, however no more than 2 regimens will be allowed prior to ASCT.

4. Male or female patients 18 years or older.

5. Patients must have an Eastern Cooperative Oncology Group (ECOG) status of 0 to 2.

6. Voluntary written informed consent before performance of any study-related procedure not part of normal medical care, with the understanding that consent may be withdrawn by the subject at any time without prejudice to future medical care.

7. Female patients who:

- Are postmenopausal for at least 1 year before the Screening visit, OR
- Are surgically sterile, OR
- If they are of childbearing potential, agree to practice 2 effective methods of contraception, at the same time, from the time of signing the informed consent, during study treatment and for 28 days after the last dose of study treatment, OR agree to completely abstain from heterosexual intercourse

Male patients, even if surgically sterilized (ie, status postvasectomy), who:

- Agree to practice effective barrier contraception during the entire study treatment period and through 28 days after the last dose of study treatment, OR
- Agree to completely abstain from heterosexual intercourse

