**Suggested Dose Modification If on lenalidomide 15 mg**

After 3 cycle is if the Lenalidomide has been increased to 15 mg daily use the following dose modification:

	Lenalidomide	MLN 9708
Dose -1	10 mg q 28	3mg
Dose -2	10 mg q 28	2.4mg
Dose -3	10 mg q 21	2.4mg
Dose -4	10 mg po q 21	1.5mg
Dose -5	5 mg q 21	1.5mg

For dosing recommendations upon recovery, refer to Table 3-2 and Table 3-3.

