### 3.3.5 Treatment Modifications for MLN9708-related AEs (Non-Hematologic Toxicities)

Treatment modifications due to MLN9708-related AEs are outlined in Table 3-3.

**Table 3-3 MLN9708 Treatment Modification (Delays, Reductions, and Discontinuations) Due to Adverse Events (Non-Hematologic Toxicities)**

Adverse Event (Severity)	Action on Study Drug	Further Considerations
Grade 1 peripheral neuropathy	
 
• No action
 
	Grade 1 signs and symptoms: asymptomatic; without pain or loss of function; clinical or diagnostic observations only[6]
New or worsening Grade 1 peripheral neuropathy with pain or Grade 2	
 
• Hold study drug until resolution to Grade <math>\leq</math> 1 or baseline
 
	Grade 2 signs and symptoms: Moderate symptoms; limiting instrumental activities of daily living (ADL)[6]
New or worsening Grade 2 peripheral neuropathy with pain or Grade 3	
 
• Hold study drug until resolution to Grade <math>\leq</math> 1 or baseline
 
• Reduce study drug to next lower dose upon recovery
 
	Grade 3 signs and symptoms: severe symptoms; limiting self-care ADL; assistive device indicated[6]
New or worsening Grade 4 peripheral neuropathy	
 
• Discontinue study drug
 
	
Grade 3 nonhematologic toxicity judged to be related to study drug	
 
• Hold study drug until resolution to Grade <math><</math> 1 or baseline
 
	Symptomatic recommendations noted in Section 3.4
If not recovered to <math><</math> Grade 1 or baseline within 4 weeks	
 
• Reduce study drug 1 to next lower dose upon return to <math><</math> Grade 1 or baseline
 
	
Subsequent recurrence Grade 3 that does not recover to <math><</math> Grade 1 or baseline within 4 weeks	
 
• Hold study drug until resolution to Grade <math><</math> 1 or baseline
 
• Reduce study drug to next lower dose
 
	Monitor closely, take appropriate medical precautions, and provide appropriate symptomatic care
Grade 4 nonhematologic toxicities judged to be related to study drug	
 
• Permanently discontinuing study drug
 
	

Once MLN9708 is reduced for any toxicity, the dose may not be re-escalated

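### The dose-reduction ladder for patients raised to lenalidomide 15 mg assumes MLN9708 is still at 3 mg, so for an already-reduced patient it conflicts with the ban on MLN9708 re-escalation

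*Combined protocol and SAP*

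**What the plan says.** Section 3.1 sets the optional increase. "Study drug will begin at Lenalidomide (10 mg/day); after three cycles", the physician may raise lenalidomide if ANC is at least 1000/µL, platelets are at least 100,000/µL and non-hematologic toxicity is no worse than grade 1: "then the dose may be increased to 15 mg/day at discretion of physician". It sets no condition on earlier reductions of either drug. MLN9708 starts at 3 mg on Days 1, 8 and 15.

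Two ladders of suggested dose modifications follow Section 3.3.3.1. In the one for patients on lenalidomide 10 mg, Dose -1 leaves lenalidomide unchanged and lists MLN9708 2.4 mg. The other is introduced with: "After 3 cycle is if the Lenalidomide has been increased to 15 mg daily use the following dose modification". Its Dose -1 row lists lenalidomide 10 mg with MLN9708 3 mg, and it closes by sending the reader to Tables 3-2 and 3-3 for dosing on recovery.

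Table 3-1 gives MLN9708 steps in one direction only: 3.0, 2.4, 1.5 mg, then discontinuation. The note under Table 3-3 (Section 3.3.5) reads: "Once MLN9708 is reduced for any toxicity, the dose may not be re-escalated". It stands beneath the non-hematologic table, but its wording covers any toxicity.

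**The concern.** A patient can reach 15 mg of lenalidomide with MLN9708 already below 3 mg. If toxicity then occurs, the ladder written for that situation names an MLN9708 dose above the one being taken, as the response to the toxicity. A prescriber who opens the ladder and a prescriber who opens Table 3-3 are told different things.

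Two features of the plan add weight. The formal toxicity stopping rule in Section 5 counts only events in cycle 1, whereas the increase comes after three cycles, so the increase criteria and the ladder carry the protection for this step. Tolerability is also a secondary objective in Section 2.2. If physicians resolve the contradiction differently, part of the variation in delivered MLN9708 dose will come from the wording of the protocol and not from patients' tolerance.

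**Working it through.** The plan has no figure of its own to reproduce here. The inputs are its tabulated doses.

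**Step 1. Can a reduced patient qualify for 15 mg?**
- Under Dose -1 of the 10 mg ladder, the patient is on lenalidomide 10 mg and MLN9708 2.4 mg. Once counts and toxicity have recovered, every condition in Section 3.1 can be met.
- A hematologic route exists as well. Table 3-2 lets MLN9708 restart one level lower after platelets at or below 30 × 10⁹/L or ANC at or below 0.75 × 10⁹/L on a dosing day.
- A patient at 1.5 mg with lenalidomide still at 10 mg is possible through two steps of Table 3-1. That needs two reductions before the increase and is presumably less common.

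**Step 2. What does each ladder row list, compared with the current MLN9708 dose?**
Change = listed dose ÷ current dose − 1.

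| Row | MLN9708 listed | Current 3.0 mg | Current 2.4 mg | Current 1.5 mg |
|---|---|---|---|---|
| 15 mg ladder, -1 | 3.0 mg | no rise | 3.0/2.4 − 1 = **+25%** | 3.0/1.5 − 1 = **+100%** |
| 15 mg ladder, -2 | 2.4 mg | no rise | no rise | 2.4/1.5 − 1 = **+60%** |
| 15 mg ladder, -3 | 2.4 mg | no rise | no rise | **+60%** |
| 15 mg ladder, -4 | 1.5 mg | no rise | no rise | no rise |
| 15 mg ladder, -5 | 1.5 mg | no rise | no rise | no rise |
| 10 mg ladder, -1 | 2.4 mg | no rise | no rise | **+60%** |
| 10 mg ladder, -2 | 2.4 mg | no rise | no rise | **+60%** |
| 10 mg ladder, -3 | 1.5 mg | no rise | no rise | no rise |
| 10 mg ladder, -4 | 1.5 mg | no rise | no rise | no rise |

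In the 15 mg ladder, no row conflicts with the ban for a patient at 3 mg, one of five does at 2.4 mg, and three of five do at 1.5 mg. In the 10 mg ladder, two of four rows conflict, and only for a patient at 1.5 mg.

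**Step 3. Size per cycle.** With three doses per 28-day cycle, the 2.4 mg patient goes from 3 × 2.4 = 7.2 mg to 3 × 3.0 = 9.0 mg, a rise of 1.8 mg or 25%.

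**Step 4. Where the assumption lies.** Dose -1 of the 15 mg ladder is lenalidomide 10 mg with MLN9708 3 mg. Reading its 28 as daily dosing through the cycle, this is the study's starting combination. The row makes sense as undoing the increase in a patient never reduced. For a patient already reduced, it also undoes the earlier MLN9708 reduction.

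**The case against.** The strongest reply is that no careful prescriber would raise MLN9708 in response to toxicity. The ladder is headed as suggested and refers onward to Tables 3-2 and 3-3, and the ban is categorical. Table 3-1 only steps down. Section 3.3.3 asks that each event be attributed to a drug where possible, so that the right one is adjusted. Lower rows do fit reduced patients: Dose -2 suits someone on 15 mg with 2.4 mg, and Dose -4 someone on 1.5 mg. Physician discretion applies throughout, and footnote 7 of the Section 8.1 flow chart adds Day 8 and Day 15 assessments in the cycle of escalation.

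All of that stands and limits the point. It does not remove the contradiction. The sentence introducing the 15 mg ladder tells the reader to use it, nothing says to enter at the row matching the current MLN9708 dose, and the onward reference puts a conflicting instruction beside it.

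Three stronger readings are tempting and are not supported:
- **That the lenalidomide increase itself causes a forbidden MLN9708 re-escalation.** Section 3.1 changes lenalidomide only. The fault is in the ladder layout, and the 10 mg ladder shares it.
- **That the increase contradicts entry by admitting growth-factor-supported counts.** The entry condition, "No growth factors within 5 days", belongs to entry. The new-cycle criteria in Section 3.3.3.1 do not repeat it, and Section 3.5.1 permits growth factors on study. The increase rule is silent on the matter, which is not a conflict. It is also stricter than the new-cycle rule on platelets (100,000 against 75,000).
- **That renal function is ignored, so 15 mg approaches a maximum tolerated exposure.** Creatinine below 2.5 mg/dL is required before the first dose, chemistry including creatinine is scheduled in later cycles, and a creatinine rise graded above 1 as a toxicity would block the increase. The background statement that "those with mild renal impairment had an AUC 56% greater than those with normal renal function" comes without sample size or spread. The 25 mg/day cohort that might serve as comparator had three patients with relapsed disease. Only stable baseline impairment is left unaddressed.

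**Conclusion.** The contradiction is real, specific and safety-relevant, but narrow. For a patient whose MLN9708 was reduced before the lenalidomide increase, the 15 mg ladder read literally lists a rise of 25% (from 2.4 mg) or of 60% to 100% (from 1.5 mg), which the note under Table 3-3 forbids. It takes three things together: an earlier MLN9708 reduction, a later toxicity at 15 mg, and literal use of a suggested table. The documents give no rate of MLN9708 reduction on this regimen, so the number of patients affected cannot be estimated, and no effect on PFS can be shown.

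Two gaps are secondary. The increase criteria do not say whether growth-factor-supported counts qualify or whether stable renal impairment bears on the decision. The lenalidomide background on special populations also refers to a precautions section on renal impairment that is not found in the document as supplied. These are matters to clarify, not contradictions.

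**What to change.** Reconcile Section 3.1, both suggested-modification ladders, Table 3-1 and the note under Table 3-3, so that the protocol gives one consistent instruction on two questions: whether a patient with an earlier MLN9708 reduction may receive the lenalidomide increase, and which ladder row applies at each current MLN9708 dose (3.0, 2.4 or 1.5 mg). Treat the 10 mg ladder in the same edit. The investigator decides what the rule is; this review takes no view on the dose.

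In the same amendment, state whether growth-factor support and stable renal impairment bear on the increase, and resolve or delete the renal cross-reference.

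The cost is amendment wording. Counts, creatinine and current doses are already collected each cycle, so no new assessments are needed. Depending on the investigator's decision, somewhat fewer patients may be eligible for the optional increase.
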